
Given these findings, we next asked whether other immune regulatory markers were increased following immunization. Splenocytes from animals treated with a DNA vaccine encoding native or optimized SSX2 were collected and antigen-specific CD3⁺CD8⁺ T cells were assessed for

expression of PD-1, TIM-3, LAG3, BTLA, CD160, or CD244. As shown in Figure 5, in addition to PD-1, expression of TIM-3 and LAG3 were also increased on T cells following immunization with the modified construct. Expression of CD244 was higher on tetramer⁺ cells from animals immunized with the native vaccine than with the control or modified construct. These findings demonstrate that combining T-cell regulatory receptor blockade with anti-PD-1 with a T-cell activating therapy (DNA vaccine) is a rational clinical direction, and this is the primary endpoint of this trial. Moreover, our murine studies suggest that other regulatory receptors might also be affected by immunization, and hence the evaluation of this will be an exploratory endpoint of this trial.

In further preclinical studies to evaluate the possible role of PD-1 in patients who previously received a DNA vaccine encoding PAP, we used a delayed-type hypersensitivity (DTH) model (developed by UW investigator [name], PhD) to evaluate mechanisms of immune regulation, similar to studies we have previously reported [57]. While a small number, we have found in 2 of 2 patients evaluated prior to and after DNA vaccination that PD-1 blockade, like CTLA-4 blockade, could restore effector function (as measured by DTH) of PAP-specific T cells elicited with vaccination (Figure 6). We also found in a patient previously treated with pTVG-HP, who then subsequently received sipuleucel-T for metastatic disease, that PD-L1 expression could be directly detected on circulating CD45⁺EpCAM⁺ cells (Figure 7). These studies form the basis for further exploratory studies proposed, to determine whether the *trans vivo* DTH method used can identify patients with antigen-specific PD-1-mediated regulation as either a predictive biomarker or measure of response, and whether similarly the presence of PD-L1 can be detected on circulating epithelial (tumor) cells as a predictive biomarker or measure of response, similar to what has been proposed for other studies using PD-1 blocking antibodies [18].

[figure not shown]
[figure not shown]

Figure 1: Modification by DNA vaccine do
Groups of 6 HHD-subcutaneously with immunized weekly wit (pTVG-SSX2, red), “optimized” epitopes (pTVG-SSX expression. As shown, animals immunized with either DNA vaccine encoding SSX2 (native or both modified epitopes) had increased PD-L1 expression on tumors relative to controls. immunized with the native DNA vaccine.

2+ tumor-bearing vaccines elicits PD-1 expression. As shown, animals immunized with either DNA vaccine encoding SSX2 (native or both modified epitopes) had increased PD-L1 expression on tumors relative to controls.

[figure not shown]

Figure 3: Immunization of mice with optimized SSX2-encoding DNA vaccine elicits higher PD-1 expression on antigen-specific CD8+ T cells. Splenocytes from animals immunized with pTVG-SSX2 (SSX-2) or pTVG-SSX2^{opt} (Optimized) were stained for p103 and p41 (HLA-A2) tetramers and PD-1. Shown is the mean fluorescence intensity (MFI) of PD-1 expression on antigen-specific CD3+CD8+tetramer+ (tetramer+) cells compared with CD3+CD8+tetramer- (CD8) populations. As shown, animals immunized with the optimized vaccine had increased PD-1 expression on antigen-specific CD8+ T cells.

[figure not shown]

Figure 4: Immunization of mice with optimized SSX2-encoding DNA vaccine with anti-PD-1 elicits greater anti-tumor response. Groups of 4-6 HLA-A2 transgenic mice were implanted subcutaneously with 2×10^4 Sarc/SSX2 tumor cells and then immunized weekly with 100 μ g plasmid DNA encoding SSX2 (pTVG-SSX2), or encoding SSX2 containing both “optimized” epitopes (pTVG-SSX2^{opt}), or vector control (pTVG4), as in Figure 4, and with or without 100 μ g anti-mouse PD-1 (clone G4) administered 24 hours after each immunization. Tumor growth was followed over time. As shown, the anti-tumor efficacy of the “optimized” vaccine was improved with anti-PD1, and no anti-tumor effect was seen with anti-PD1 treatment alone.

[figure not shown]

Figure 5: Immunization of mice with APL-modified SSX2-encoding DNA vaccine elicits PD-1 and TIM-3 expressing tetramer+ CD8+ T cells. Groups of 4-6 HLA-A2 transgenic mice were implanted subcutaneously with 2×10^4 Sarc/SSX2 tumor cells and then immunized weekly with 100 μ g plasmid DNA encoding SSX2 (pTVG-SSX2), or encoding SSX2 containing both APL-modified epitopes (pTVG-SSX2^{opt}), or vector control (pTVG4), as in Figure 4. Splenocytes recovered from animals were stained for tetramer positive events among CD8+ T cells and costained for the markers indicated. Top panels represent p41-specific tetramer positive events, bottom panels represent p103-specific tetramer positive events. Of note, tetramer positive events are detectable in mice with Sarc/SSX2 tumors even with control immunization (pTVG4); these events not detectable in non-tumor bearing mice (not shown).

[figure not shown]

Figure 6: Patients treated with pTVG-HP develop T cell responses to PAP, the function of which is regulated by PD-1. PBMC obtained from 2 patients pre (blue) or 2 weeks post (red) a 12-week treatment with pTVG-HP were placed in the footpads of SCID mice with the 1 μg of the antigens listed (TT/D = tetanus toxoid, positive control, PSA = negative control), with or without 1 μg of anti-CTLA-4 or anti-PD1. DTH responses were read at 24 hours. As shown, both patients had responses to PAP after immunization that were “uncovered” by either CTLA-4 or PD-1 blockade.

[figure not shown]

Figure 7: PD-L1 can be detected directly on circulating epithelial cells (presumed circulating tumor cells) by flow cytometry. PBMC were obtained from a patient who had previously received pTVG-HP, and then subsequently received standard sipuleucel-T for the treatment of metastatic prostate cancer. Cells were stained for CD45, EpCAM, and PD-L1. The gating shows live (DAPI) CD45-EpCAM⁺ cells (a population not detectable in non-cancer population – not shown) for their PD-L1 expression.

F. Summary

The current protocol will examine the use of a plasmid DNA vaccine encoding PAP to induce and/or augment therapeutic T-cells specific for the prostate tumor antigen PAP in patients with castrate-resistant, metastatic prostate cancer with concurrent or subsequent treatment with a PD pathway inhibitor, pembrolizumab. The primary endpoint, objective response, is based on observations from previous early phase clinical trials demonstrating no objective disease response in patients treated with PD-1 blockade alone, and our preliminary studies demonstrating that in a similar murine model of tumor cells that express PD-L1 that there was no evidence of tumor growth delay or eradication unless PD pathway blockade was combined with tumor antigen-specific vaccination. This trial will explore whether there is a preferred sequence of treatment, and will in secondary and exploratory endpoints evaluate whether sequential or concurrent treatment affects the character and magnitude of the immune response. Further studies will explore whether the identification of antigen-specific PD-1-regulated T-cells is predictive for response to combined treatment. An additional exploratory endpoint will be to identify whether changes in FLT PET scans, particularly in systemic lymph nodes or lymph nodes in the area of immunization, might serve as a molecular imaging tool to identify immunological activation following immunization with or without pembrolizumab. The trial will be conducted in patients with castrate-resistant, metastatic prostate cancer, as this is the lethal form of prostate cancer and one for which there is a high need for therapies with a greater safety profile and greater magnitude of benefit. Moreover, based on published studies, the median time to disease progression in this stage

of disease is on the order of 3 months, and few PSA responses have been observed following vaccination alone in published studies in this stage of disease [7, 58], simplifying the identification of potential benefit, and potential magnitude of such benefit, for planning future confirmatory clinical trials.

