Vaccine / Treatment Visit:	SCREENING		Day 1	Day 15 (+/- 3 days)	Day 22 (7 +/- 3 days after day 15)	Day 29 (14 +/- 3 days after day 15)	Day 43 (14 +/- 3 days after day 29)	Day 57 (14 +/- 3 days after day 43)	Day 64 (7 +/- 3 days after day 57)	Day 71 (14 +/- 3 days after day 57)	Day 85 (14 +/- 3 days after day 71) – 3 month	Day 106 (21 +/- 3 days after day 85)	Day 127 (21 +/- 3 days after day 106)	Day 148 (21 +/- 3 days after day 127)	Day 169 (21 +/- 3 days after day 148) – 6 m	9-month F/U (84 +/- 10 days after day 169)	OFF STUDY 12-month F/U – (84 +/- 10 days after 9month
	Within 6 weeks of day 1	Within 4 weeks of day 1															
History and Physical Exam																	
History	X																
Consent	X																
Physical Exam, ECOG PS		X	X		X		X		X		X	X	X	X	X	X	X
Tox assessment ^a		X	X	X	X	X	X	X	X	X	X	X	X	X	X	X	X
Lab Tests																	
CBC	X		X		X		X		X		X ^g	X	X	X	X	X	X
Chemistry panel ^f	X		X		X		X		X		X ^g	X	X	X	X	X	X
PT/INR		X ^k									X ^k						
Serum testosterone	X																
PSA and PAP	X		X		X		X		X		X ^g	X	X	X	X	X	X
Procedures																	
CT chest/abdomen/pelvis	X										X ^{gj}				X ^{hj}	X ^{hj}	X ^{ij}
Bone scan ^l	X										X ^g				X ^h	X ^h	X ⁱ
Leukapheresis		X ^b													X ^{bh}		
FLT PET scan ^m		X ^c									X ^g						
Tissue biopsy ^m		X ^d									X ^g						
Tetanus immunization		X ^e															
Blood for immune analyses		X					X				X				X	X	X
Blood for CTC analysis		X					X				X				X	X	X
Treatments																	
DNA immunization			X	X		X	X	X		X							
Pembrolizumab infusion			X		X		X		X								

^a Study coordinator or research nurse review of systems

^b For patients unable to undergo leukapheresis, a 200-mL blood draw (green top tubes) may be performed instead

^c FLT PET scan – within 4 weeks (28 days) of day 1 – to provide baseline study for comparison prior to treatment

^d Biopsy within 2 weeks prior to day 1

^e Tetanus immunization to take place any time after leukapheresis and prior to day 1

^f Where chemistry labs indicated, the following serum tests are to be performed: Chem 7 (sodium, potassium, bicarbonate, BUN, creatinine, glucose), ALT, AST, bilirubin, alkaline phosphatase, amylase, TSH (thyroid stimulating hormone), and LDH

^g Procedures can be +/- 7 days of this visit, scans to be done prior to biopsy (and study treatment for Arm 2)

^h Can be +/- 7 days of this visit

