ⁱ Can be +/- 7 days of this visit, and not required if this is off-study visit and previous scans already confirmed disease progression

^j CT of chest at this time point only as clinically indicated

^k PT/INR only required for those subjects who will be undergoing a biopsy. May be performed up to 30 days prior to biopsy, required same day if subject is on coumadin

^l If NaF PET/CT is available as standard of care procedure, this may be substituted for bone scan (bone scintigraphy), however all pre-treatment and post-treatment tests must use the same modality (NaF PET/CT or bone scintigraphy)

^m See section 9 for whether or not biopsy and FLT PET is required

Plan of Treatment: ARM 2

Vaccine / Treatment Visit:	SCREENING		Day 1	Day 15 (+/- 3 days)	Day 29 (14 +/- 3 days after day 15)	Day 43 (14 +/- 3 days after day 29)	Day 57 (14 +/- 3 days after day 43)	Day 71 (14 +/- 3 days after day 57)	Day 85 (14 +/- 3 days after day 71) – 3 month	Da 106 (21 +/- 3 days after day 85)	Da 127 (21 +/- 3 days after day 106)	Day 148 (21 +/- 3 days after day 127)	Day 169 (21 +/- 3 days after day 148) – 6 m	9-month F/U (84 +/- 10 days after day 169)	OF F STUDY 12-month F/U – (84 +/- 10 days after 9month F/U)
	Within 6 weeks of day 1	Within 4 weeks of day 1													
History and Physical Exam															
History	X														
Consent	X														
Physical Exam, ECOG PS		X	X			X			X	X	X	X	X	X	X
Tox assessment ^a		X	X	X	X	X	X	X	X	X	X	X	X	X	X
Lab Tests															
CBC	X		X			X			X ^g	X	X	X	X	X	X
Chemistry panel ^f	X		X			X			X ^g	X	X	X	X	X	X
PT/INR		X ^k							X ^k						
Serum testosterone	X														
PSA and PAP	X		X			X			X ^g	X	X	X	X	X	X
Procedures															
CT chest/abdomen/pelvis	X								X ^{gi}				X ^{hj}	X ^{hj}	X ^{ij}
Bone scan ^l	X								X ^g				X ^h	X ^h	X ⁱ
Leukapheresis		X ^b											X ^{bh}		
FLT PET scan ^m		X ^c							X ^g						
Tissue biopsy ^m		X ^d							X ^g						
Tetanus immunization		X ^e													
Blood for immune analyses		X				X			X ^g				X	X	X
Blood for CTC analysis		X				X			X ^g				X	X	X
Treatments															
DNA immunization			X	X	X	X	X	X							
Pembrolizumab infusion									X	X	X	X			

^a Study coordinator or research nurse review of systems

^b For patients unable to undergo leukapheresis, a 200-mL blood draw (green top tubes) may be performed instead

^c FLT PET scan – within 4 weeks (28 days) of day 1 – to provide baseline study for comparison prior to treatment

^d Biopsy within 2 weeks prior to day 1

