^e Tetanus immunization to take place any time after leukapheresis and prior to day 1

^f Where chemistry labs indicated, the following serum tests are to be performed: Chem 7 (sodium, potassium, bicarbonate, BUN, creatinine, glucose), ALT, AST, bilirubin, alkaline phosphatase, amylase, TSH (thyroid stimulating hormone), and LDH

^g Procedures can be +/- 7 days of this visit; scans to be done prior to biopsy (and study treatment for Arm 2)

^h Can be +/- 7 days of this visit

ⁱ Can be +/- 7 days of this visit, and not required if this is off-study visit and previous scans already confirmed disease progression

^j CT of chest at this time point only as clinically indicated

^k PT/INR only required for those subjects who will be undergoing a biopsy. May be performed up to 30 days prior to biopsy, required same day if subject is on coumadin^l If NaF PET/CT is available as standard of care procedure, this may be substituted for bone scan (bone scintigraphy), however all pre-treatment and post-treatment tests must use the same modality (NaF PET/CT or bone scintigraphy)

^m See section 9 for whether or not biopsy and FLT PET is required.

Plan of Treatment: ARM 3 – EXTENDED TREATMENT COHORT

Vaccine / Treatment Visit:	SCREENING		Day 1	Week 3 (21 +/- 3 days from Day 1)	Week 6 (21 +/- 3 days from week 3)	Week 9 (21 +/- 3 days from week 6)	Week 12 (21 +/- 3 days from week 9)	Week 15 (21 +/- 3 days from week 12)	Week 18 (21 +/- 3 days from week 15)	Week 21 (21 +/- 3 days from week 18)	Week 24 (21 +/- 3 days from week 21)	Week 27 (21 +/- 3 days from week 24)	Week 30 (21 +/- 3 days from week 27)	Week 33 (21 +/- 3 days from week 30)	Week 36 (21 +/- 3 days from week 33)	Week 39 (21 +/- 3 days from week 36)	Week 42 (21 +/- 3 days from week 39)	Week 45 (21 +/- 3 days from week 42)	END OF STUDY Week 48 (21 +/- 3 days after week 45)	28-Day Follow Up (28 +/- 7 days after off-treatment visit)
	Within 6 wks of day 1	Within 4 wks of day 1																		
History and Physical Exam																				
History	X																			
Consent	X																			
Physical Exam, ECOG PS		X	X		X		X		X		X		X		X		X		X	X
Tox assessment ^a		X	X	X	X	X	X	X	X	X	X	X	X	X	X	X	X	X	X	X
Lab Tests																				
CBC	X		X	X ⁱ	X ⁱ	X ⁱ	X ⁱ	X ⁱ	X ⁱ	X ⁱ	X ⁱ	X ⁱ	X ⁱ	X ⁱ	X ⁱ	X ⁱ	X ⁱ	X ⁱ	X ⁱ	X
Chemistry panel ^f	X		X	X ⁱ	X ⁱ	X ⁱ	X ⁱ	X ⁱ	X ⁱ	X ⁱ	X ⁱ	X ⁱ	X ⁱ	X ⁱ	X ⁱ	X ⁱ	X ⁱ	X ⁱ	X ⁱ	X
PT/INR		X ^k					X ^k													
Serum testosterone	X																			

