1. Subjects will receive pTVG-HP DNA immunizations intradermally on the deltoid area of the lateral arm (preferentially left arm) with 0.25 mL administered at each of two adjacent sites.
 2. Following vaccinations, the subjects will be observed for 60 minutes for unanticipated adverse events.
- M. 3-Month Follow-up - Day 85 (14 +/- 3 days after day 71 visit)
1. Physical examination, symptoms assessment, and ECOG performance score.
 2. Blood draw for CBC, chemistry panel, serum PSA and PAP (can be performed +/- 7 days of this visit)
 3. 10 ml peripheral blood (red-top tubes) for sera to evaluate antibody responses, and 100 ml peripheral blood (green-top heparinized tubes) for T-cell response evaluation and CTC analysis (can be performed +/- 7 days of this visit)
 4. CT scan of abdomen and pelvis, bone scintigraphy (can be performed +/- 7 days of this visit, but prior to pembrolizumab treatment for patients in Arm 2)
 5. FLT PET/CT scan (can be performed +/- 7 days of this visit, but prior to pembrolizumab treatment for patients in Arm 2)
 6. Tissue biopsy of same metastatic lesion as in pre-treatment period (can be performed +/- 7 days of this visit, but prior to pembrolizumab treatment for patients in Arm 2)

ARM 2 SUBJECTS ONLY – Anti-PD-1 #1:

7. Pembrolizumab 2 mg/kg administered intravenously over 30 minutes
8. Subjects will be observed for an additional 30 minutes for unanticipated adverse events. Vital signs (temperature, heart rate and blood pressure) will be assessed and recorded by the staff prior to, and at the end of, the treatment period.

N. DAY 106 – (21 +/- 3 days after day 85 visit):

1. Physical examination, symptoms assessment, and ECOG performance score.
2. Blood draw for CBC, chemistry panel, serum PSA and PAP

ARM 2 SUBJECTS ONLY – Anti-PD-1 #2:

3. Pembrolizumab 2 mg/kg administered intravenously over 30 minutes
4. Subjects will be observed for an additional 30 minutes for unanticipated adverse events. Vital signs (temperature, heart rate and blood pressure) will be assessed and recorded by the staff prior to, and at the end of, the treatment period.

O. DAY 127 – (21 +/- 3 days after day 106 visit):

1. Physical examination, symptoms assessment, and ECOG performance score.
2. Blood draw for CBC, chemistry panel, serum PSA and PAP

ARM 2 SUBJECTS ONLY – Anti-PD-1 #3:

3. Pembrolizumab 2 mg/kg administered intravenously over 30 minutes

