3'-Deoxy-3'-[¹⁸F]Fluorothymidine (FLT) positron emission tomography (PET)/computed tomography (CT) uses a thymidine analogue that accumulates in proliferating tissue. Proliferating tissue could include malignant lesions or immune cells. Following vaccination we have observed a proliferation of CD4+ and CD8+ T cells specific for PAP, at least as assessed *in vitro* following reencounter with the PAP antigen [29, 31]. In a study of patients with melanoma treated intranodally with a dendritic cell vaccine, FLT PET/CT could detect uptake in treated lymph nodes compared to control lymph nodes following vaccination, uptake that persisted for up to 3 weeks [78]. Consequently, FLT PET/CT may be useful as a molecular imaging tool to detect immune activation after immunization, at the same time as detecting decreases in proliferating tumor masses as a result of treatment. We hypothesize that FLT PET/CT will be able to detect increased uptake in left axillary draining lymph nodes (draining site of intradermal immunization) at 12 weeks compared with pre-treatment studies, and that a decrease in uptake will be observed in soft tissue metastatic deposits. FLT PET/CT will be performed at baseline (within 4 weeks of starting treatment) and at week 12, thus enabling comparative evaluation with other imaging obtained at that time and biopsy results.

FLT PET/CT IMAGING PROCEDURES: To ensure uniformity as well as optimal data interpretation, analyses will be conducted under the supervision of [name], PhD (co-investigator) at the University of Wisconsin Image Analysis Core (IMAC) facility, with all radiographic analysis by [name] and designees blinded to study treatment arm.

- At the beginning of each imaging session, a CT scan will be obtained on the combined PET/CT scanner. The CT scan is an integral part of the PET/CT acquisition and serves for attenuation correction calculations and better PET/CT image co-registration. It will enable better delineation of the patient anatomy, which will be important when comparing different scans. An FLT-PET scan will follow. The patients will be injected up to 15 mCi (555 MBq) of ¹⁸F-FLT.

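### At Day 85, Arm 2 research blood may be drawn after the first pembrolizumab dose, and the permitted FLT PET windows differ between Arms 1 and 2

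*Combined protocol and SAP*

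**What the plan says.** The Arm 2 calendar's footnote g reads "Procedures can be +/- 7 days of this visit; scans to be done prior to biopsy (and study treatment for Arm 2"), and the Arm 1 calendar has the same rule: "Procedures can be +/- 7 days of this visit, scans to be done prior to biopsy (and study treatment for Arm 2"). Its treatment-order clause names scans only.

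Section 9 covers both arms under "M. 3-Month Follow-up - Day 85 (14 +/- 3 days after day 71 visit"). Items 4 to 6 (CT and bone scan, FLT PET, biopsy) each carry the condition "can be performed +/- 7 days of this visit, but prior to pembrolizumab treatment for patients in Arm 2". Item 3, the research blood, has only "for T-cell response evaluation and CTC analysis (can be performed +/- 7 days of this visit"). Items 7 and 8 of the same visit are the first Arm 2 infusion. Arm 1 has no treatment on that day.

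The calendars treat the blood differently. In the row "Blood for immune analyses", and in the CTC row, the Day 85 cell carries footnote g in Arm 2 but no footnote in Arm 1, whereas 9.M item 3 gives both arms the same 7 days either side.

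On analysis:

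- Section 10.B puts the primary immune analysis at 6 months and makes the other time points secondary.
- Section 11.F.6.1 compares CTC numbers between arms at each time point.
- Section 11.F.6.7 compares FLT changes between arms by t-test or rank-sum test, with no term for days since vaccination.
- Section 10.E cites an earlier study of a dendritic cell vaccine given into the node, in which node FLT showed "uptake that persisted for up to 3 weeks".

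**The concern.** Arm 2's research blood is scheduled pre-treatment and at Days 43, 85 and 169, then at 9 and 12 months. Day 43 is the visit of the fourth vaccination. By Day 169 all four pembrolizumab doses have been given. Day 85 is therefore the only planned sample that shows the full six-dose vaccine course without the antibody. The plan protects the scans and the biopsy at that visit from pembrolizumab exposure but not the blood that accompanies them. Any draw after the infusion mixes exposed samples into what a reader of the results would take as a vaccine-only group.

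The FLT point is separate. The before-pembrolizumab condition rightly keeps Arm 2 scans unexposed, but it also cuts off the second half of the Arm 2 window. Arm 1 keeps the full window. If node uptake falls with time since vaccination, a later average scan in Arm 1 could produce or hide a between-arm difference that pembrolizumab did not cause.

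**Working it through.** The plan states no figure for this contrast, so there is nothing to reproduce first. The check is arithmetic on the permitted windows.

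**Research blood (9.M item 3).** The window is -7 to +7 days, which is 15 calendar days. The Arm 2 infusion is at day 0. Days +1 to +7, or 7 of the 15, fall after it, so permitted exposure at the draw is 0 to 7 days. This counts permitted days; it does not estimate how often they are used.

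**Days from last vaccine to FLT scan.** The last vaccine is at Day 71 in both arms, and the visit is 14 +/- 3 days later.

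Lag = 14 + v + s, where v runs from -3 to +3, and s from -7 to +7 (Arm 1) or -7 to 0 (Arm 2).

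- Arm 1: 14 - 3 - 7 = 4 to 14 + 3 + 7 = 24 days.
- Arm 2: 4 to 14 + 3 + 0 = 17 days.
- At the nominal visit day (v = s = 0), both arms are at 14 days.

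**Mean lag if every permitted day is equally likely (assumption).** The mean of s is 0 in Arm 1 and -3.5 in Arm 2, giving 14.0 and 10.5 days. Of the 7 x 15 = 105 Arm 1 combinations, 28 (27%) fall after day 17, the last possible Arm 2 day, and 6 (5.7%) fall after day 21.

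**Patients who also have a biopsy.** Footnote g puts the scan before the biopsy in both arms. Taking all pairs with the scan on or before the biopsy as equally likely, the mean of s is -7 + 14/3 = -2.33 in Arm 1 and -7 + 7/3 = -4.67 in Arm 2. The mean lags are 11.7 and 9.3 days, a gap of 2.3 days instead of 3.5.

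**Node signal with no pembrolizumab effect.** The documents give no decay curve, so each row is an assumption. Signals are fractions of peak, averaged over the lags above.

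| Assumed curve | Arm 1 | Arm 2 | Ratio, Arm 2 / Arm 1 | Ratio, scan before biopsy |
|---|---|---|---|---|
| Linear, 1 - t/21, zero after day 21 | 0.34 | 0.50 | 1.48 | 1.25 |
| Half-life 7 days | 0.28 | 0.37 | 1.33 | 1.21 |
| Half-life 10 days | 0.40 | 0.49 | 1.23 | 1.15 |
| Half-life 14 days | 0.51 | 0.60 | 1.17 | 1.11 |
| Plateau through day 21, then zero | 0.94 | 1.00 | 1.06 | 1.01 |

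The direction is the same in every row. The size runs from about 1.0 to 1.5.

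**The case against.** The strongest reply is that a permitted window is not an observed schedule. Arm 2's FLT window lies wholly inside Arm 1's, the nominal day is identical, and nothing in the documents says Arm 1 scans were booked late. A reader might infer that the FLT contrast is mistimed; the text supports only that it could be. The cited persistence also comes from a different vaccine and route, and a plateau reading leaves almost no difference. All of this stands.

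The analyses are also modest in standing. FLT and CTC are exploratory. FLT is required in up to 6 subjects per arm, where a two-sided 0.05 t-test has 80% power only for a difference of about 1.8 SD. The stated node hypothesis is a change from pre-treatment, and F.6.7 covers soft tissue lesions as well as nodes. This stands too.

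A reader might take secondary objective 2 to be a 12-week comparison of vaccine with and without pembrolizumab. It is not: it concerns concurrent versus delayed scheduling, and F.5.2 names no 12-week contrast. Arm 2 also has an earlier unexposed sample at Day 43, though not after the full vaccine course.

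Nor does the argument extend to Arm 3. It is non-randomized and every patient receives pembrolizumab from Day 1, so its scan timing has no bearing on the Arm 1 versus Arm 2 contrast.

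Finally, Section 2.F reports 11 Arm 3 patients by January 2018, and Section 6.A closes Arms 1 and 2 once they have at least 12 evaluable subjects and Arm 3 is open. New windows will change little for those arms. That argues for an analysis remedy alongside the wording change. None of these replies meets the gap in 9.M item 3.

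**Conclusion.** The research-blood gap holds on the text alone and needs no modelling: up to 7 days of pembrolizumab exposure is allowed at Arm 2's only sample after six vaccines and before the drug. It can affect the secondary Day 85 immune comparisons and the exploratory CTC comparison at that time point.

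The FLT asymmetry holds as a property of the permitted windows (4-24 versus 4-17 days after the last vaccine) and is unadjusted in F.6.7. Its consequence is conditional. The 3.5-day mean gap (2.3 days with a biopsy) assumes even use of the windows, and the signal ratio of about 1.0 to 1.5 rests on assumed curves. The documents do not show that any scan was mistimed.

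No primary endpoint, sample size or 6-month immune analysis changes. The severity is low, and the correction costs little.

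**What to change.** 1. In Section 9.M, give item 3 the same condition as items 4 to 6: "can be performed +/- 7 days of this visit, but prior to pembrolizumab treatment for patients in Arm 2". Extend the treatment-order clause of footnote g to research blood, and reconcile the Day 85 blood cells of the two calendars with item 3.
2. For any Arm 1 patient still to be scanned, use the Arm 2 window for FLT PET: from 7 days before the visit to the day of the visit. Both arms would then span 4-17 days after the last vaccine, and the expected gap under even use falls from 3.5 days to 0.
3. For samples and scans already obtained, use the detailed SAP that Section 11.F.1 says will be written before the final analysis. It should flag or exclude Arm 2 Day 85 research blood drawn after the infusion. It should also report days since last vaccine by arm, or adjust for them, in the F.6.7 node comparison.

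The cost is slightly tighter scheduling (Arm 1 FLT goes from 15 permitted days to 8) and a small sensitivity analysis. No extra scan, biopsy or blood draw is needed.
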